15.3 Appendix 3 – Definition of Migraine Days

Migraine Day: Any calendar day in which the subject experiences a qualified migraine headache (onset, continuation, or recurrence of the migraine headache). A qualified migraine headache is defined as a migraine with or without aura, lasting for ≥ 30 minutes, and meeting at least one of the following criteria (a and/or b)

a) ≥ 2 of the following pain features:

- Unilateral location,
- Pulsating quality (throbbing),
- Moderate or severe pain intensity,
- Aggravation by or causing avoidance of routine physical activity (e.g. walking or climbing stairs)

b) ≥ 1 of the following associated symptoms:

- Nausea and/or vomiting
- Photophobia and phonophobia

If the subject took a migraine-specific medication (i.e., study medication [open-label, extension phase only], triptan or ergotamine) during aura or to treat headache on a calendar day, then it will be counted as a migraine day regardless of the duration and pain features/associated symptoms. The use of study medication on non-scheduled dosing days is only permitted during the open-label, extension phase; **dosing with study medication on non-scheduled dosing days is not permitted during the double-blind, treatment phase.**

A moderate to severe migraine day is a migraine day with a migraine reported with moderate or severe pain intensity.

Headache Day: Any calendar day in which the subject experiences a qualified headache (initial onset, continuation, or recurrence of the headache). A qualified headache is defined as:

- a qualified migraine headache (including an aura-only event that is treated with acute migraine-specific medication), or
 - a qualified non-migraine headache, which is a headache that lasts ≥ 30 minutes and is not a qualified migraine headache, or
 - a headache of any duration for which acute headache treatment is administered.
-

Acute Migraine-specific Medication Treatment Day: Any calendar day during which the subject took a migraine-specific medication (i.e., study medication [open-label, extension phase only], triptan or ergotamine). The use of study medication on non-scheduled dosing days is only permitted during the open-label, extension phase; **dosing with study medication on non-scheduled dosing days is not permitted during the double-blind, treatment phase.**

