#### 6.2.6.1 *Study Medication*

The eDiary has multiple sources of study drug exposure. Subjects are required to report study drug date/times and doses in the following 4 eDiary sources as appropriate: (1) study medication from the scheduled dosing report; (2) study medication to treat headache or aura from the evening report headache log; (3) additional study medication to treat headache or aura from the evening report headache log; or (4) study medication to treat headache or aura from the follow-up headache log. In addition, sites may report study drug dates and doses in the eDiary medication reconciliation form from missed scheduled dosing reports or evening report headache logs.

Imputed OL rimegepant to treat headache date/time will be derived for subjects who answer “yes” to the question about having already taken study medication to treat a headache on the eDiary scheduled dosing report, but do not have study drug data from any other eDiary source on the same day. Subjects with non-missing imputed OL rimegepant to treat headache date/times will be credited with taking 1 tablet of OL rimegepant on each of those days to account for missed OL rimegepant exposure from eDiary non-compliance. Otherwise, if no study drug data were reported in the eDiary on a given day (i.e., missing study drug date/time), then it is assumed that the subject did not take study drug that day. See Section 7.3 for derived dates.

A by-subject listing will present eDiary exposure (i.e., number of tablets taken) and drug accountability for randomized subjects. This listing will include all drug accountability data including treatment (DB rimegepant; DB placebo; OL rimegepant) corresponding to the kit ID, but only eDiary records with non-missing study drug start date/time and number of tablets > 0. The eDiary subcategory of question (scheduled dosing report; evening report headache log [study medication; additional study medication]; follow-up headache log; and medication reconciliation form) will also be displayed. COVID-19 visit impact code for visits impacted by COVID-19 will also be displayed (see Section 9.1.5.2).

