### **7.3 Derived Dates**

Derived dates for defining analysis periods are defined as follows:

---

- eDiary reference time/point date/time: See Section 7.6.2.1.
  - eDiary dosing dates:
    - Study drug to treat headache or during aura date/time: Complete reference time point date/time from any of the following date/time questions: study medication to treat headache or during aura from the evening report headache log or follow-up headache log; additional study medication to treat headache or during aura from the evening report headache log.
    - Imputed OL rimegepant to treat headache date/time: Complete reference time point date/time from “yes” response to question about having already taken study medication to treat headache from the scheduled dosing report. Derived only if both of the following criteria are met:
      - Reference time point date/time on or after the IWRS Week 12 kit assigned local date/time
      - There are no complete reference time point dates on the same day as the “yes” response from any of the following questions: study medication to treat headache or during aura date/time from the evening report headache log or follow-up headache log; additional study medication to treat headache or during aura date/time from the evening report headache log; date of missed scheduled dosing report or evening report headache log from the medication reconciliation form; study medication date/time from the scheduled dosing report.
    - Study drug date/time: Study drug to treat headache or during aura date/time, imputed OL rimegepant to treat headache date/time, or complete reference time point date/time from any of the following questions: date of missed scheduled dosing report or evening report headache log from the medication reconciliation form (note that time is not collected); study medication date/time from the scheduled dosing report.
      - DBT: Reference time point date/time before the IWRS Week 12 kit assigned local date/time (reference time point date before the IWRS Week 12 kit assigned local date for medication reconciliation form data) or the IWRS Week 12 kit assigned local date/time missing
      - OL rimegepant: Reference time point date/time on or after the IWRS Week 12 kit assigned local date/time (reference time point date on or after the IWRS Week 12 kit assigned local date for medication reconciliation form data)
    - Study drug start date/time: Earliest study drug date/time.

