    - Non-study medication triptan and ergotamine parameters: The reference time point date/time will be set to the last non-missing headache start date/time from evening report headache logs with finding date/time  $\leq 24$  hours at or before the follow-up headache log finding date/time.
    - Study medication for headache parameters with the same finding date/time: The reference time point date/time will be set to the study medication for headache or aura date/time, if not missing.
      - Parameters will include the following: study medication for headache or aura (yes, no); study medication for headache or aura date/time; number of tablets taken; confirm number of tablets taken (yes, no).
  - Scheduled dosing report parameters with the same finding date/time: The reference time point date/time will be set to the study medication date/time, if not missing.
-

- Parameters will include the following: took study medication today (yes, no); study medication date/time; number of tablets taken; confirm number of tablets taken (yes, no).
- Medication reconciliation form date missed and number of tablets taken parameters with the same finding date/time: The reference time point date/time will be set to the date missed, if not missing. Note that time will be missing.

Otherwise, the reference time point date/time will be set to the eDiary finding date/time.

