#### 7.6.2.2 eDiary Migraine Days

For migraine day analyses, a day of efficacy data is defined as any non-missing eDiary efficacy date (see Section 7.3).

A migraine day is defined as a day of efficacy data with either (1) or (2):

- 1) Qualified migraine headache based on the following criteria per BHV3000-305 Protocol Appendix 3:
  - “Yes” response to the question about having a headache# with complete reference time point date/time#, or non-missing headache start date/time# (see Section 7.3)
  - Lasting for  $\geq 30$  minutes, defined as any of the following:
    - “Yes” response to the question about the headache lasting  $\geq 30$  minutes#
    - Headache end date/time# – headache start date/time#  $\geq 30$  minutes, where headache end date/time and headache start date/time have the same finding date/time
    - Finding date/time# – headache start date/time#  $\geq 30$  minutes and headache end status is still continuing#, where headache start date/time and headache end status have the same finding date/time
    - Headache end date/time@ – headache start date/time#  $\geq 30$  minutes, where headache end date/time is from the follow-up headache log with earliest finding date/time  $\leq 24$  hours on or after the finding date/time of a still continuing headache from the evening report headache log
  - Meeting at least one of the following criteria (a or b):

- a.  $\geq 2$  of the following pain features based on “yes” response to questions with the same finding date/time:
    - i. Unilateral location#,
    - ii. Pulsating quality (throbbing)#,
    - iii. Moderate or severe pain intensity#
    - iv. Aggravation by or causing avoidance of routine physical activity (e.g. walking or climbing stairs)#
  - b.  $\geq 1$  of the following associated symptoms based on “yes” response to questions with the same finding date/time:
    - i. Nausea#
    - ii. Vomiting#
    - iii. Both photophobia# and phonophobia#
- 2) No qualified migraine headache but meeting either of the following criteria:
- a. Non-missing date/time of (1) study drug to treat headache or during aura#@ during the on-DBT efficacy analysis period, or (2) OL rimegepant on a non-scheduled day during the on-OL rimegepant efficacy analysis period (see Sections 7.3 and 7.6.2.3).

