- Block 2: All days on or after the first switch but before the second switch are considered to follow the second planned EOD dosing pattern. If there is only 1 switch, then all days on or after the first switch are considered to follow the second planned EOD dosing pattern.
- Block 3: All days on or after the second switch but before the third switch are considered to follow the initial planned EOD dosing pattern. If there are only 2 switches, then all days on or after the second switch are considered to follow the initial planned EOD dosing pattern.

This iterative process continues as needed.

Example:

- Subject has 26 days in the on-OL rimegepant efficacy analysis period, i.e., OL rimegepant start date on day 0 and OL rimegepant last date + 1 on day 25.
  - Scheduled report dates fall on planned OL rimegepant days 0, 2, 4, 8, 9, 11, 15, 18, 22, and 24.
    - The initial EOD dosing schedule pattern is even.
    - There are 2 switches: day 9 is the first switch and day 18 is the second switch.
    - All even days from 0 to 8 inclusive (i.e., days 0, 2, 4, 6, 8) are scheduled days.
    - All odd days from 9 to 17 inclusive (i.e., days 9, 11, 13, 15, 17) are scheduled days.
    - All even days from 18 to 24 inclusive (i.e., 18, 20, 22, 24) are scheduled days.
-

- All other days (i.e., days 1, 3, 5, 7, 10, 12, 14, 16, 19, 21, 23, and 25) are non-scheduled days.

Note that (1) imputed OL rimegepant dates and (2) OL rimegepant dates from the scheduled dosing report can only be on scheduled days. OL rimegepant dates from the evening report headache log, follow-up headache log, or medication reconciliation form can be on scheduled or non-scheduled days.

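### In the open-label extension, the SAP's dose-based migraine-day rule (7.6.2.2, criterion 2a) does not implement the protocol's Appendix 3 definition, and the departure is not declared

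*SAP*

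**What the plan says.** **Protocol, Appendix 3 (15.3).** A day without a qualified migraine headache still counts if a migraine-specific medication was taken "during aura or to treat headache on a calendar day, then it will be counted as a migraine day". In the OLE, study medication is one of these medications. The condition is the reason for the dose. The definition does not limit the day to a scheduled or non-scheduled one.

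**SAP 7.6.2.2, criterion 2.** Limb (1) of 2a, for the double-blind phase, counts "study drug to treat headache or during aura#@ during the on-DBT efficacy analysis period". Limb (2), for the OLE, counts "OL rimegepant on a non-scheduled day during the on-OL rimegepant efficacy analysis period" and states no reason for the dose. Criterion 2b keeps the headache-or-aura condition for triptans and ergotamine in both phases.

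**Where OL rimegepant dates come from.** SAP 7.3 includes medication reconciliation form dates. SAP 6.2.6.1 says that "sites may report study drug dates and doses in the eDiary medication reconciliation form from missed scheduled dosing reports or evening report headache logs". For such a record, SAP 7.6.2.1 states: "The reference time point date/time will be set to the date missed, if not missing".

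**Which days they can fall on.** SAP 7.6.2.3 says "OL rimegepant dates from the scheduled dosing report can only be on scheduled days", and the same holds for imputed dates. In contrast, "OL rimegepant dates from the evening report headache log, follow-up headache log, or medication reconciliation form can be on scheduled or non-scheduled days".

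**Linked rule.** Limb (2) of the efficacy-date definition in SAP 7.3 makes an OL rimegepant date on a non-scheduled day an efficacy date by itself.

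**Declaration and timing.** SAP section 8 states that there are no changes to the protocol's planned analyses. The revision history shows that criterion 2a and the efficacy-date definition were both modified in version 10.0, after the final database lock.

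**The concern.** Appendix 3 asks why the tablet was taken. SAP limb (2) asks on which derived calendar day it fell. The two questions can give different answers in both directions:

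- A preventive dose recorded only on the reconciliation form, and dated on a derived non-scheduled day, is counted as a migraine day although no headache was reported.
- A dose taken for headache or aura on a scheduled day is not counted under 2a, although Appendix 3 counts it. The SAP expects such doses: 7.3 derives an imputed date from a subject's answer on the scheduled dosing report that study medication had already been taken for headache, and 7.6.2.3 places those dates on scheduled days only.

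The outputs at stake are OLE migraine days per month and the OLE responder percentages against the observational period. These are exploratory objectives, and OLE efficacy is a stated focus of the Addendum Report (SAP section 4). A reader who relies on section 8 would assume that those tables use the Appendix 3 definition.

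**Working it through.** **1. Reproduce the SAP's own example (7.6.2.3).** Scheduled reports fall on days 0, 2, 4, 8, 9, 11, 15, 18, 22 and 24, in a period running from day 0 to day 25 (26 days). The gaps are 2, 2, 4, 1, 2, 4, 3, 4, 2. The odd gaps end on days 9 and 18, so there are two switches. Scheduled days are 0, 2, 4, 6, 8; then 9, 11, 13, 15, 17; then 18, 20, 22, 24. That is 5 + 5 + 4 = 14, which leaves 26 − 14 = 12 non-scheduled days. Both the switches and the 12 listed days agree with the SAP.

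**2. Run late and reconciled doses through the same rule.** Take an even pattern with reports on days 0, 2 and 4, and a dose due on day 6.

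| Case | Derivation | Counted under 2a(2)? |
|---|---|---|
| (a) Taken on day 7, entered on the scheduled dosing report | Gap 7 − 4 = 3, odd: day 7 is a switch date and so scheduled | No |
| (b) Taken on day 7, on the reconciliation form only and dated day 7; next report on day 8 or day 9 | Day 8: gap 4, no switch. Day 9: gap 5, switch only from day 9. Either way day 7 is non-scheduled | Yes, with no headache recorded |
| (c) Reconciled doses dated days 7 and 9; next report on day 11 | Gap 7, switch only from day 11. Days 7 and 9 are non-scheduled | Yes, both |
| (d) Taken on day 6 as due, report missed, reconciled with date missed = day 6 | Day 6 is even and so scheduled | No |

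The exposure is therefore limited to reconciliation-form doses dated on a derived non-scheduled day.

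**3. Size for one subject-month.** SAP 6.3.1.2 gives 28 × migraine days / efficacy days. The diary counts below are assumptions for illustration. Each has one affected dose on a day with no other ground for a migraine day.

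- 28 diary days, 5 migraine days, evening report present that day: 28 × 5/28 = 5.0 without the dose; 28 × 6/28 = 6.0 with it. Added: 1.0.
- 27 diary days, 5 migraine days, no evening report that day: 28 × 5/27 = 5.19 without; 28 × 6/28 = 6.0 with, because the dose also creates an efficacy day. Added: 0.81.
- 14 diary days, 2 migraine days, evening report present that day: 28 × 2/14 = 4.0 without; 28 × 3/14 = 6.0 with. Added: 2.0.

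The illustrative range is about 0.8 to 2.0 days per 28.

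**4. Two threshold effects.** A month with 13 diary days is not evaluable. One off-pattern dose on a day without a diary entry makes it 14, so the month enters the analysis; with 2 migraine days it enters at 28 × 3/14 = 6.0. Separately, in a month with no migraine days, one such dose turns a 100% responder for total migraine days into a failure.

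**5. Size at group level.** If a proportion f of evaluable subjects had one such dose in a month, each adding 1.0 day, the monthly mean would rise by f days: 0.01 at an assumed 1%, 0.10 at an assumed 10%. One subject among the estimated 675 entering the OLE gives 1/675 ≈ 0.0015. The documents give no frequency.

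**The case against.** **The rule is a reasonable proxy.** Protocol 7.2.2 permits a non-scheduled OLE dose only to treat a migraine, so a dose on such a day suggests headache treatment. This stands as a rationale, but the SAP does not state it. The proxy also assumes adherence and a correctly derived calendar, at the point where diary reporting has already failed.

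**Reconciled doses should carry the missed report's date.** If the form always gives the due date of the missed scheduled report, the dose stays on a scheduled day, as in case (d). Other off-pattern entries would then come from missed headache logs, which are headache treatment. Much of this stands: cases (b) and (c) need an off-pattern date, and the SAP describes pattern switches as rare. But SAP 6.2.6.1 speaks of study drug dates, 7.6.2.3 says that form dates can be non-scheduled, and the derivation does not separate the two kinds of missed report.

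**Stronger readings that the documents do not support:**

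- A reader might infer that late scheduled doses in general become migraine days. Case (a) shows that they do not when entered on the scheduled dosing report.
- A reader might infer a bias against rimegepant. The omission of headache doses on scheduled days works the other way, so the net direction is not established.
- A reader might infer that the rule alone makes OLE values non-comparable with the observational period. Neither limb of 2a, nor 2b, applies in that period, so an asymmetry exists already and would survive any repair here.
- A reader might set the added day beside the planned 1-day treatment effect. One is a single subject-month, the other a difference between group means.
- A fully shifted month of every-other-day doses could in theory add 28/2 = 14 days. That needs every dose to be off-pattern, recorded only by reconciliation, with no intervening scheduled report and no overlap with true migraine days. Nothing suggests that this occurs.

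**Conclusion.** The concern holds in a limited form. For the OLE, SAP criterion 2a(2) is not the Appendix 3 definition. It admits off-pattern reconciliation-form doses without headache or aura, it leaves out headache or aura doses on scheduled days, and section 8 does not disclose either departure. The change to the criterion after database lock makes that disclosure more important. It does not show that the rule was chosen for its results.

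One affected dose is worth roughly 0.8 to 2.0 days in that subject's 28-day count, under the assumed diary counts. The effect on group summaries rests on a frequency that the documents do not give, and its net sign is unknown. A dose-only day with no reported severity enters total migraine days. It does not enter the moderate-or-severe count, though it can add to that denominator.

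The primary endpoint and all hierarchically tested endpoints are confined to the double-blind phase and are unaffected. What changes is the meaning of exploratory, descriptive OLE tables. The repair is worth making because it is specific and cheap.

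**What to change.** **Preferred.** Restate 2a(2) to count OL rimegepant on any OLE day, scheduled or not, when the evening or follow-up headache log records it as taken to treat headache or during aura. Add reconciliation records that can be identified as missed headache logs. Align limb (2) of the efficacy-date definition in SAP 7.3, and state whether the imputed headache-treatment dates count. First check that the form identifies which report was missed: SAP 7.6.2.1 names only the missed date and the number of tablets.

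**Alternative.** Keep the current rule, declare it in section 8 with its rationale, report how many OLE migraine days rest only on reconciliation-form doses, and add a sensitivity table of OLE migraine days and responder rates without those doses.

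Reconciliation-only doses should not simply be dropped from the main analysis. The form also recovers missed headache logs, so dropping them all would remove genuinely treated migraines.

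**Cost.** SAP wording and a rerun of the OLE tables; no new data collection. Some treated migraines whose reconciliation record cannot be classified would be left out of one version of the tables.

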### 7.6.2.3 *Scheduled and Non-Scheduled Days in the OLE Phase*

All days in the on-OL rimegepant efficacy analysis period are classified as either scheduled or non-scheduled days. Scheduled days are defined as days in the planned EOD dosing schedule. All other days are considered to be non-scheduled days.

For each OL rimegepant treated subject, the initial planned EOD dosing schedule pattern is classified as even or odd with respect to the OL rimegepant start date as follows:

- Calculate planned OL rimegepant day = scheduled report date – OL rimegepant start date for each scheduled report date in the on-OL rimegepant efficacy analysis period.

- A scheduled report date is a complete eDiary finding date from a “yes” response to either (1) question about having already taken study medication today to treat headache from the scheduled dosing report, or (2) question about taking a scheduled dose of study medication today from the scheduled dosing report.
- If the first planned OL rimegepant day is an even number or missing, then the initial planned EOD dosing schedule pattern is even.
- If the first planned OL rimegepant day is an odd number, then the initial planned EOD dosing schedule pattern is odd.

It is expected that scheduled days follow the initial planned EOD dosing schedule for the entire OLE phase. Thus, if the initial planned EOD dosing schedule pattern is even, then it is expected that scheduled days are all even planned OL rimegepant days 0, 2, 4, etc. Otherwise, if the initial planned EOD dosing schedule pattern is odd, then it is expected that scheduled days are all odd planned OL rimegepant days 1, 3, 5, etc.

However, in rare cases, the eDiary may reset at scheduled report dates and switch planned EOD dosing schedule patterns. For example, the planned EOD dosing schedule may start as even, switch to odd, and then switch back to even. A switch date is defined as a scheduled report date with an odd number of days between it and the previous scheduled report date. Switch dates define blocks of days within the on-OL rimegepant efficacy analysis period as follows:

- Block 1: All days in the OL rimegepant efficacy analysis period before the first switch are considered to follow the initial planned EOD dosing pattern.
- Block 2: All days on or after the first switch but before the second switch are considered to follow the second planned EOD dosing pattern. If there is only 1 switch, then all days on or after the first switch are considered to follow the second planned EOD dosing pattern.
- Block 3: All days on or after the second switch but before the third switch are considered to follow the initial planned EOD dosing pattern. If there are only 2 switches, then all days on or after the second switch are considered to follow the initial planned EOD dosing pattern.

This iterative process continues as needed.

Example:

- Subject has 26 days in the on-OL rimegepant efficacy analysis period, i.e., OL rimegepant start date on day 0 and OL rimegepant last date + 1 on day 25.
  - Scheduled report dates fall on planned OL rimegepant days 0, 2, 4, 8, 9, 11, 15, 18, 22, and 24.
    - The initial EOD dosing schedule pattern is even.
    - There are 2 switches: day 9 is the first switch and day 18 is the second switch.
    - All even days from 0 to 8 inclusive (i.e., days 0, 2, 4, 6, 8) are scheduled days.
    - All odd days from 9 to 17 inclusive (i.e., days 9, 11, 13, 15, 17) are scheduled days.
    - All even days from 18 to 24 inclusive (i.e., 18, 20, 22, 24) are scheduled days.
-

- All other days (i.e., days 1, 3, 5, 7, 10, 12, 14, 16, 19, 21, 23, and 25) are non-scheduled days.

Note that (1) imputed OL rimegepant dates and (2) OL rimegepant dates from the scheduled dosing report can only be on scheduled days. OL rimegepant dates from the evening report headache log, follow-up headache log, or medication reconciliation form can be on scheduled or non-scheduled days.

